### **5.3 METHODS AND TIMING FOR CAPTURING AND ASSESSING SAFETY PARAMETERS**

The investigator is responsible for ensuring that all adverse events (see Section 5.2.1 for definition) are recorded on the Adverse Event eCRF and reported to the Sponsor in accordance with instructions provided in this section and in Sections 5.4–5.6.

For each adverse event recorded on the Adverse Event eCRF, the investigator will make an assessment of seriousness (see Section 5.2.2 for seriousness criteria), severity (see Section 5.3.3), and causality (see Section 5.3.4).

#### **5.3.1 Adverse Event Reporting Period**

Investigators will seek information on adverse events at each patient contact. All adverse events, whether reported by the patient or noted by study personnel, will be recorded in the patient's medical record and on the Adverse Event eCRF.

**After informed consent** has been obtained **but prior to initiation of study drug**, only serious adverse events caused by a protocol-mandated intervention (e.g., invasive procedures such as biopsies, discontinuation of medications) should be reported (see Section 5.4.2 for instructions for reporting serious adverse events).

**After initiation of study drug**, all adverse events will be reported until 30 days after the last dose of study drug.

Instructions for reporting adverse events that occur after the adverse event reporting period are provided in Section 5.6.

### 5.3.2 Eliciting Adverse Event Information

A consistent methodology of non-directive questioning should be adopted for eliciting adverse event information at all patient evaluation timepoints. Examples of non-directive questions include the following:

"How have you felt since your last clinic visit?"

"Have you had any new or changed health problems since you were last here?"

### 5.3.3 Assessment of Severity of Adverse Events

The adverse event severity grading scale for the NCI CTCAE v4.0 will be used for assessing adverse event severity. Table 6 will be used for assessing severity for adverse events that are not specifically listed in the NCI CTCAE v4.0.

**Table 6 Adverse Event Severity Grading Scale for Events Not Specifically Listed in NCI CTCAE**

Grade	Severity
1	Mild; asymptomatic or mild symptoms; clinical or diagnostic observations only; or intervention not indicated
2	Moderate; minimal, local, or non-invasive intervention indicated; or limiting age-appropriate instrumental activities of daily living a
3	Severe or medically significant, but not immediately life-threatening; hospitalization or prolongation of hospitalization indicated; disabling; or limiting self-care activities of daily living b, c
4	Life-threatening consequences or urgent intervention indicated d
5	Death related to adverse event d

NCI CTCAE = National Cancer Institute Common Terminology Criteria for Adverse Events.

Note: Based on the most recent version of NCI CTCAE (v4.0), which can be found at: [http://ctep.cancer.gov/protocolDevelopment/electronic\\_applications/ctc.htm](http://ctep.cancer.gov/protocolDevelopment/electronic_applications/ctc.htm)

- a Instrumental activities of daily living refer to preparing meals, shopping for groceries or clothes, using the telephone, managing money, etc.
- b Examples of self-care activities of daily living include bathing, dressing and undressing, feeding oneself, using the toilet, and taking medications, as performed by patients who are not bedridden.
- c If an event is assessed as a "significant medical event," it must be reported as a serious adverse event (see Section 5.4.2 for reporting instructions), per the definition of serious adverse event in Section 5.2.2.
- d Grade 4 and 5 events must be reported as serious adverse events (see Section 5.4.2 for reporting instructions), per the definition of serious adverse event in Section 5.2.2.

### 5.3.4 Assessment of Causality of Adverse Events

Investigators should use their knowledge of the patient, the circumstances surrounding the event, and an evaluation of any potential alternative causes to determine whether an

adverse event is considered to be related to the study drug, indicating "yes" or "no" accordingly. The following guidance should be taken into consideration:

- Temporal relationship of event onset to the initiation of study drug
- Course of the event, with special consideration of the effects of dose reduction, discontinuation of study drug, or reintroduction of study drug (as applicable)
- Known association of the event with the study drug or with similar treatments
- Known association of the event with the disease under study
- Presence of risk factors in the patient or use of concomitant medications known to increase the occurrence of the event
- Presence of non-treatment-related factors that are known to be associated with the occurrence of the event

For patients receiving combination therapy, causality will be assessed individually for each protocol-mandated therapy.

### **5.3.5 Procedures for Recording Adverse Events**

Investigators should use correct medical terminology/concepts when recording adverse events on the Adverse Event eCRF. Avoid colloquialisms and abbreviations.

Only one adverse event term should be recorded in the event field on the Adverse Event eCRF.

#### **5.3.5.1 Infusion-Related Reactions**

Adverse events that occur during or within 24 hours after study drug administration and are judged to be related to study drug infusion should be captured as a diagnosis (e.g., "infusion-related reaction" on the Adverse Event eCRF. If possible, avoid ambiguous terms such as "systemic reaction." Associated signs and symptoms should be recorded on the dedicated Infusion-Related Reaction eCRF. If a patient experiences both a local and systemic reaction to the same dose of study drug, each reaction should be recorded separately on the Adverse Event eCRF, with signs and symptoms also recorded separately on the dedicated Infusion-Related Reaction eCRF.

#### **5.3.5.2 Diagnosis versus Signs and Symptoms**

For adverse events other than IRRs (see Section 5.3.5.1), a diagnosis (if known) should be recorded on the Adverse Event eCRF rather than individual signs and symptoms (e.g., record only liver failure or hepatitis rather than jaundice, asterixis, and elevated transaminases). However, if a constellation of signs and/or symptoms cannot be medically characterized as a single diagnosis or syndrome at the time of reporting, each individual event should be recorded on the Adverse Event eCRF. If a diagnosis is subsequently established, all previously reported adverse events based on signs and symptoms should be nullified and replaced by one adverse event report based on the single diagnosis, with a starting date that corresponds to the starting date of the first symptom of the eventual diagnosis.

### **5.3.5.3 Adverse Events That Are Secondary to Other Events**

In general, adverse events that are secondary to other events (e.g., cascade events or clinical sequelae) should be identified by their primary cause, with the exception of severe or serious secondary events. A medically significant secondary adverse event that is separated in time from the initiating event should be recorded as an independent event on the Adverse Event eCRF. For example:

- If vomiting results in mild dehydration with no additional treatment in a healthy adult, only vomiting should be reported on the eCRF.
- If vomiting results in severe dehydration, both events should be reported separately on the eCRF.
- If a severe gastrointestinal hemorrhage leads to renal failure, both events should be reported separately on the eCRF.
- If dizziness leads to a fall and consequent fracture, all three events should be reported separately on the eCRF.
- If neutropenia is accompanied by an infection, both events should be reported separately on the eCRF.

All adverse events should be recorded separately on the Adverse Event eCRF if it is unclear as to whether the events are associated.

### **5.3.5.4 Persistent or Recurrent Adverse Events**

A persistent adverse event is one that extends continuously, without resolution, between patient evaluation timepoints. Such events should only be recorded once on the Adverse Event eCRF. The initial severity (intensity or grade) of the event will be recorded at the time the event is first reported. If a persistent adverse event becomes more severe, the most extreme severity should also be recorded on the Adverse Event eCRF. If the event becomes serious, it should be reported to the Sponsor immediately (i.e., no more than 24 hours after learning that the event became serious; see Section 5.4.2 for reporting instructions). The Adverse Event eCRF should be updated by changing the event from "non-serious" to "serious," providing the date that the event became serious, and completing all data fields related to serious adverse events.

A recurrent adverse event is one that resolves between patient evaluation timepoints and subsequently recurs. Each recurrence of an adverse event should be recorded as a separate event on the Adverse Event eCRF.

### **5.3.5.5 Abnormal Laboratory Values**

Not every laboratory abnormality qualifies as an adverse event. A laboratory test result must be reported as an adverse event if it meets any of the following criteria:

- Is accompanied by clinical symptoms
- Results in a change in study treatment (e.g., dosage modification, treatment interruption, or treatment discontinuation)

- Results in a medical intervention (e.g., potassium supplementation for hypokalemia) or a change in concomitant therapy
- Is clinically significant in the investigator's judgment

Note: For oncology trials, certain abnormal values may not qualify as adverse events.

It is the investigator's responsibility to review all laboratory findings. Medical and scientific judgment should be exercised in deciding whether an isolated laboratory abnormality should be classified as an adverse event.

If a clinically significant laboratory abnormality is a sign of a disease or syndrome (e.g., ALP and bilirubin  $5 \times$  ULN associated with cholestasis), only the diagnosis (i.e., cholestasis) should be recorded on the Adverse Event eCRF.

If a clinically significant laboratory abnormality is not a sign of a disease or syndrome, the abnormality itself should be recorded on the Adverse Event eCRF, along with a descriptor indicating whether the test result is above or below the normal range (e.g., "elevated potassium," as opposed to "abnormal potassium"). If the laboratory abnormality can be characterized by a precise clinical term per standard definitions, the clinical term should be recorded as the adverse event. For example, an elevated serum potassium level of 7.0 mEq/L should be recorded as "hyperkalemia."

Observations of the same clinically significant laboratory abnormality from visit to visit should only be recorded once on the Adverse Event eCRF (see Section 5.3.5.4 for details on recording persistent adverse events).

### **5.3.5.6 Abnormal Vital Sign Values**

Not every vital sign abnormality qualifies as an adverse event. A vital sign result must be reported as an adverse event if it meets any of the following criteria:

- Is accompanied by clinical symptoms
- Results in a change in study treatment (e.g., dosage modification, treatment interruption, or treatment discontinuation)
- Results in a medical intervention or a change in concomitant therapy
- Is clinically significant in the investigator's judgment

It is the investigator's responsibility to review all vital sign findings. Medical and scientific judgment should be exercised in deciding whether an isolated vital sign abnormality should be classified as an adverse event.

If a clinically significant vital sign abnormality is a sign of a disease or syndrome (e.g., high blood pressure), only the diagnosis (i.e., hypertension) should be recorded on the Adverse Event eCRF.

Observations of the same clinically significant vital sign abnormality from visit to visit should only be recorded once on the Adverse Event eCRF (see Section 5.3.5.4 for details on recording persistent adverse events).

#### **5.3.5.7 Abnormal Liver Function Tests**

The finding of an elevated ALT or AST ( $> 3 \times$  baseline value) in combination with either an elevated total bilirubin ( $> 2 \times$  ULN) or clinical jaundice in the absence of cholestasis or other causes of hyperbilirubinemia is considered to be an indicator of severe liver injury (as defined by Hy's law). Therefore, investigators must report as an adverse event the occurrence of either of the following:

- Treatment-emergent ALT or AST  $> 3 \times$  baseline value in combination with total bilirubin  $> 2 \times$  ULN (of which  $\geq 35\%$  is direct bilirubin)
- Treatment-emergent ALT or AST  $> 3 \times$  baseline value in combination with clinical jaundice

The most appropriate diagnosis or (if a diagnosis cannot be established) the abnormal laboratory values should be recorded on the Adverse Event eCRF (see Section 5.3.5.2) and reported to the Sponsor immediately (i.e., no more than 24 hours after learning of the event), either as a serious adverse event or an adverse event of special interest (see Section 5.4.2).

#### **5.3.5.8 Deaths**

For this protocol, mortality is an efficacy endpoint. Deaths that occur during the protocol-specified adverse event reporting period (see Section 5.3.1) that are attributed by the investigator solely to progression of cancer should be recorded on the Death Attributed to Progressive Disease eCRF. All other deaths that occur during the adverse event reporting period, regardless of relationship to study drug, must be recorded on the Adverse Event eCRF and immediately reported to the Sponsor (see Section 5.4.2).

Death should be considered an outcome and not a distinct event. The event or condition that caused or contributed to the fatal outcome should be recorded as the single medical concept on the Adverse Event eCRF. Generally, only one such event should be reported. If the cause of death is unknown and cannot be ascertained at the time of reporting, "**unexplained death**" should be recorded on the Adverse Event eCRF. If the cause of death later becomes available (e.g., after autopsy), "unexplained death" should be replaced by the established cause of death. If the cause of death is unknown and cannot be ascertained at the time of reporting, "**unexplained death**" should be recorded on the Adverse Events eCRF. If the cause of death later becomes available (e.g., after autopsy), "unexplained death" should be replaced by the established cause of death. The term "**sudden death**" should not be used unless combined with the presumed cause of death (e.g., "sudden cardiac death").

Deaths that occur after the adverse event reporting period should be reported as described in Section 5.6.

### **5.3.5.9 Preexisting Medical Conditions**

A preexisting medical condition is one that is present at the screening visit for this study. Such conditions should be recorded on the General Medical History and Baseline Conditions eCRF.

A preexisting medical condition should be recorded as an adverse event only if the frequency, severity, or character of the condition worsens during the study. When recording such events on the Adverse Event eCRF, it is important to convey the concept that the preexisting condition has changed by including applicable descriptors (e.g., "more frequent headaches").

### **5.3.5.10 Lack of Efficacy or Worsening of Cancer**

Events that are clearly consistent with the expected pattern of progression of the underlying disease should not be recorded as adverse events. These data will be captured as efficacy assessment data only. In most cases, the expected pattern of progression will be based on RECIST v1.1 or immune-modified RECIST. In rare cases, the determination of clinical progression will be based on symptomatic deterioration. However, every effort should be made to document progression through use of objective criteria. If there is any uncertainty as to whether an event is due to disease progression, it should be reported as an adverse event.

### **5.3.5.11 Hospitalization or Prolonged Hospitalization**

Any adverse event that results in hospitalization (i.e., inpatient admission to a hospital) or prolonged hospitalization should be documented and reported as a serious adverse event (per the definition of serious adverse event in Section 5.2.2), except as outlined below.

An event that leads to hospitalization under the following circumstances should not be reported as an adverse event or a serious adverse event:

- Hospitalization for respite care
- Planned hospitalization required by the protocol (e.g., for study drug administration or insertion of access device for study drug administration)
- Hospitalization for a preexisting condition, provided that all of the following criteria are met:

The hospitalization was planned prior to the study or was scheduled during the study when elective surgery became necessary because of the expected normal progression of the disease

The patient has not experienced an adverse event

Hospitalization due solely to progression of the underlying cancer

An event that leads to hospitalization under the following circumstances is not considered to be a serious adverse event, but should be reported as an adverse event instead:

- Hospitalization that was necessary because of patient requirement for outpatient care outside of normal outpatient clinic operating hours

#### **5.4 IMMEDIATE REPORTING REQUIREMENTS FROM INVESTIGATOR TO SPONSOR**

Certain events require immediate reporting to allow the Sponsor to take appropriate measures to address potential new risks in a clinical trial. The investigator must report such events to the Sponsor immediately; under no circumstances should reporting take place more than 24 hours after the investigator learns of the event. The following is a list of events that the investigator must report to the Sponsor within 24 hours after learning of the event, regardless of relationship to study drug:

- Serious adverse events (defined in Section 5.2.2; see Section 5.4.2 for details on reporting requirements)
- Adverse events of special interest (defined in Section 5.2.3; see Section 5.4.2 for details on reporting requirements)
- Pregnancies (see Section 5.4.3 for details on reporting requirements)
- Overdoses, medication errors, drug abuse, or drug misuse (see Section 5.4.4 for details on reporting requirements)

The investigator must report new significant follow-up information for these events to the Sponsor immediately (i.e., no more than 24 hours after becoming aware of the information). New significant information includes the following:

- New signs or symptoms or a change in the diagnosis
- Significant new diagnostic test results
- Change in causality based on new information
- Change in the event's outcome, including recovery
- Additional narrative information on the clinical course of the event

Investigators must also comply with local requirements for reporting serious adverse events to the local health authority and IRB/EC.

#### **5.4.2 Reporting Requirements for Serious Adverse Events and Adverse Events of Special Interest**

##### **5.4.2.1 Events That Occur prior to Study Drug Initiation**

After informed consent has been obtained but prior to initiation of study drug, only serious adverse events caused by a protocol-mandated intervention should be reported. The paper Clinical Trial Serious Adverse Event/Adverse Event of Special Interest Reporting Form provided to investigators should be completed and submitted to the Sponsor or its designee immediately (i.e., no more than 24 hours after learning of the event), either by faxing or by scanning and emailing the form using the fax number or email address provided to investigators.

##### **5.4.2.2 Events That Occur after Study Drug Initiation**

After initiation of study drug, serious adverse events and adverse events of special interest will be reported until 30 days after the last dose of study drug. Investigators should record all case details that can be gathered immediately (i.e., within 24 hours after learning of the event) on the Adverse Event eCRF and submit the report via the electronic data capture (EDC) system. A report will be generated and sent to Roche Safety Risk Management by the EDC system.

In the event that the EDC system is unavailable, the paper Clinical Trial Serious Adverse Event/Adverse Event of Special Interest Reporting Form provided to investigators should be completed and submitted to the Sponsor or its designee immediately (i.e., no more than 24 hours after learning of the event), either by faxing or by scanning and emailing the form using the fax number or email address provided to investigators. Once the EDC system is available, all information will need to be entered and submitted via the EDC system.

Instructions for reporting serious adverse events that occur > 30 days after the last dose of study treatment are provided in Section 5.6.

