#### **4.4.2.3 Prohibited Therapy**

Use of the following concomitant therapies is prohibited as described below:

- Concomitant therapy intended for the treatment of cancer (including, but not limited to, chemotherapy, hormonal therapy, immunotherapy, radiotherapy, and herbal therapy), whether health authority–approved or experimental, is prohibited during study treatment until disease progression is documented and the patient has discontinued study treatment, with the exception of palliative radiotherapy and radiotherapy to the brain.
- Investigational therapy (other than protocol-mandated study treatment) is prohibited during study treatment.
- Treatment with live, attenuated vaccines (e.g., FluMist®) are prohibited within 4 weeks prior to initiation of study treatment, during treatment with atezolizumab, and for 5 months after the last dose of atezolizumab
- Systemic immunostimulatory agents (including, but not limited to, interferons and IL-2) are prohibited within 4 weeks or 5 half-lives of the drug, whichever is longer, prior to initiation of study treatment and during study treatment because these agents could potentially increase the risk for autoimmune conditions when given in combination with atezolizumab.

- Systemic immunosuppressive medications (including, but not limited to, prednisone, cyclophosphamide, azathioprine, methotrexate, thalidomide, and anti-TNF agents) are prohibited within 2 weeks of Cycle 1, Day 1 and during study treatment because these agents could potentially alter the efficacy and safety of atezolizumab.
- Systemic corticosteroids may not be administered as premedication to patients with an allergy to contrast agents used for tumor scans (see [Appendix 3](#) for information on tumor scans for patients with contrast allergies).

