## **5.6 ADVERSE EVENTS THAT OCCUR AFTER THE ADVERSE EVENT REPORTING PERIOD**

After the end of the adverse event reporting period (defined as 30 days after the last dose of study drug), all deaths, regardless of cause, should be reported through use of the Long-Term Survival Follow-Up eCRF. In addition, if the investigator becomes aware of a serious adverse event that is believed to be related to prior exposure to study drug, the event should be reported through use of the Adverse Event eCRF. However, if the EDC system is not available, the investigator should report these events directly to the Sponsor or its designee, either by faxing or by scanning and emailing the paper Clinical Trial Serious Adverse Event/Adverse Event of Special Interest Reporting Form using the fax number or email address provided to investigators.

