- o Ophthalmologic examination must be performed at the following timepoints only for patients on cobimetinib: at screening; on Day 1 of Cycle 2 ( $\pm 1$  week); on Day 1 of Cycles 5, 8, and 11 (every 3 treatment cycles;  $\pm 2$  weeks); on Day 1 of Cycles 15, 19, and 23 (every 4 treatment cycles;  $\pm 2$  weeks); on Day 1 of Cycles 29, 35, 41, 47, and every 6 treatment cycles thereafter (i.e., Cycles 53, 59, 65, etc.;  $\pm 2$  weeks for each); and at treatment discontinuation visit evaluation (unless evaluation performed within the previous 12 weeks showed no clinically significant findings and/or changes from baseline).
- p All women of childbearing potential will have a serum pregnancy test at screening. Urine pregnancy tests will be performed on Day 1 ( $\pm 2$  weeks) of every cycle. If a urine pregnancy test is positive, it must be confirmed by a serum pregnancy test.
- q Includes dipstick (pH, specific gravity, glucose, protein, ketones, and blood) and microscopic examination (sediment, RBCs, WBCs, casts, crystals, epithelial cells, and bacteria).
- r Includes any medication (e.g., prescription drugs, over-the-counter drugs, herbal or homeopathic remedies, nutritional supplements) used by a patient from 7 days prior to initiation of study drug until 30 days after the last dose of study drug.
- s After informed consent has been obtained but prior to initiation of study drug, only serious adverse events caused by a protocol-mandated intervention should be reported. After initiation of study drug, all adverse events will be reported until 30 days after the last dose of study drug or initiation of new anti-cancer therapy, whichever occurs first. After this period, all deaths, regardless of cause, should be reported. After this period, the Sponsor should be notified if the investigator becomes aware of any serious adverse event that is believed to be related to prior study drug treatment (see Section 5.6). The investigator should follow each adverse event until the event has resolved to baseline grade or better, the event is assessed as stable by the investigator, the patient is lost to follow-up, or the patient withdraws consent. Every effort should be made to follow all serious adverse events or adverse events of special interest considered to be related to study drug or trial-related procedures until a final outcome can be reported.

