### Schedule of Pharmacokinetic and Immunogenicity Samples

Visit	Timepoint	Sample Type(s)
Day 1 of Cycle 1 (Cohorts 1–6 only)	Prior to atezolizumab infusion	Atezolizumab PK and ADA (serum)
	30 ( $\pm$ 10) minutes following end of atezolizumab infusion	Atezolizumab PK (serum)
Day 15 of Cycle 1 (Cohort 7 only)	Prior to atezolizumab infusion	Atezolizumab PK and ADA (serum)
	30 ( $\pm$ 10) minutes following end of atezolizumab infusion	Atezolizumab PK (serum)
Day 1 of Cycles 2, 4, 8, 12, and 16	Prior to atezolizumab infusion	Atezolizumab PK and ADA (serum)
Day 15 of Cycle 3	Prior to atezolizumab infusion	Atezolizumab PK and ADA (serum)
	Prior to cobimetinib dose	Cobimetinib PK (plasma)
	30 ( $\pm$ 10) minutes following end of atezolizumab infusion	Atezolizumab PK and ADA (serum)
	2–4 hours after cobimetinib dose	Cobimetinib PK (plasma)
Atezolizumab treatment discontinuation visit	At visit	Atezolizumab PK and ADA (serum)
> 90 days after last atezolizumab infusion	At visit	Atezolizumab PK and ADA (serum)

ADA= anti-drug antibody; NA= not applicable; PK= pharmacokinetic.

Notes: Except for Day 1 of Cycle 1 all other study visits and assessments during the treatment period should be performed within  $\pm$ 3 days of the scheduled date.

Study assessments may be delayed or moved ahead of the window to accommodate holidays, vacations, and unforeseen delays.

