## **Appendix 8**

### **Risks Associated with Atezolizumab and Guidelines for Management of Adverse Events Associated with Atezolizumab**

Toxicities associated or possibly associated with atezolizumab treatment should be managed according to standard medical practice. Additional tests, such as autoimmune serology or biopsies, should be used to evaluate for a possible immunogenic etiology.

Although most immune-related adverse events observed with immunomodulatory agents have been mild and self-limiting, such events should be recognized early and treated promptly to avoid potential major complications. Discontinuation of atezolizumab may not have an immediate therapeutic effect, and in severe cases, immune-related toxicities may require acute management with topical corticosteroids, systemic corticosteroids, or other immunosuppressive agents.

The investigator should consider the benefit–risk balance a given patient may be experiencing prior to further administration of atezolizumab. In patients who have met the criteria for permanent discontinuation, resumption of atezolizumab may be considered if the patient is deriving benefit and has fully recovered from the immune-related event. Patients can be re-challenged with atezolizumab only after approval has been documented by both the investigator (or an appropriate delegate) and the Medical Monitor.

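### After reporting closes 30 days after the last dose, a new non-serious AESI has no reporting route, and a non-fatal late SAE is requested only if the investigator learns of it and believes it related

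*Combined protocol and SAP*

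**What the plan says.** **Main window.** Section 5.4.2.2: "serious adverse events and adverse events of special interest will be reported until 30 days after the last dose of study drug". Section 5.3.1 applies the same limit generally: "all adverse events will be reported until 30 days after the last dose of study drug". Neither says which of the two drugs is meant.

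**After the window.** Section 5.6 asks for deaths without a filter ("all deaths, regardless of cause, should be reported through use of the Long-Term Survival Follow-Up eCRF"). It asks for other events only "if the investigator becomes aware of a serious adverse event that is believed to be related to prior exposure to study drug". AESIs are not mentioned there.

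**Schedule of activities.** Appendix 1 footnote s gives a different closing rule: "until 30 days after the last dose of study drug or initiation of new anti-cancer therapy, whichever occurs first".

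**What the window governs.** Section 5.2.3 lists the AESIs and requires each to reach the sponsor within 24 hours. Some entries have a grade threshold (rash, diarrhoea and CPK elevation at Grade 3 or above). Pneumonitis, colitis, nephritis, myositis, vasculitis and the endocrinopathies have none. Section 6.5 reports incidence, percentages and exposure-adjusted rates of SAEs and AESIs by cohort.

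**Other rules that run past day 30.** Section 4.4.2.3 bars live vaccines "during treatment with atezolizumab, and for 5 months after the last dose of atezolizumab". Contraception (Section 4.1.1.2) and pregnancy reporting (Section 5.4.3.1) also run 5 months. Appendix 2 schedules a PK and ADA sample "> 90 days after last atezolizumab infusion".

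**The concern.** Many AESIs are on the list whatever their grade, so non-serious cases are part of the category by design. A Grade 2 pneumonitis or a new hypothyroidism must be reported within 24 hours if it starts on day 30. If it starts on day 31, nothing asks for it.

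The protocol gives no reason for a 30-day limit on immune-related events, although it keeps several other precautions after atezolizumab for 5 months and brings patients back for a sample after day 90. Appendix 8 also warns that "Discontinuation of atezolizumab may not have an immediate therapeutic effect".

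At stake are the AESI and SAE rates in Section 6.5. Safety is a stated objective and each cohort is small. As written, the rates combine systematic reporting up to day 30 with reporting afterwards that depends on seriousness, awareness and one investigator's view of causality in an open-label study. The two closing rules also mean that sites could stop reporting at different times.

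**Working it through.** The plan gives no figure for late events, so there is nothing to reproduce. The check sets the reporting rules side by side.

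**1. Which new events are requested, by onset** (Sections 5.2.3, 5.3.1, 5.4.2.2 and 5.6)

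| New event | Up to day 30 | After day 30 |
|---|---|---|
| Death | recorded | recorded, any cause |
| Non-fatal SAE, believed related | reported | reported if the investigator becomes aware |
| Non-fatal SAE, judged unrelated | reported | not requested |
| Non-serious AESI | reported within 24 hours | no route |

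The gap is the last two rows, plus any related SAE that nobody hears about. Events that start inside the window are not affected: Section 5.5.1 follows them until they resolve or stabilise.

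**2. Contacts available after day 30**
- Survival follow-up every 3 months (Appendix 1), first at about day 91 if counted from the last dose. The adverse-event row is marked in this column, but footnote s keeps the awareness rule.
- The PK/ADA visit after day 90. The adverse-event row has no mark here. Footnote c calls the visit one not specified by the protocol, although Appendix 2 schedules it.
- Tumour assessments every 8 weeks for patients who stopped for reasons other than progression (Section 3.1.1.2).

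**3. Length of the window against the protocol's 5-month precautions**
Five months is 150 to 153 days.
- Share covered: 30/150 = 20.0% to 30/153 = 19.6%.
- Days not covered: 150 − 30 = 120 to 153 − 30 = 123.
- If collection ran to day 90: 90/150 = 60.0% to 90/153 = 58.8%.

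These figures compare one protocol rule with another. They do not measure drug effect.

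**4. Which clock**
Section 3.1.1.1 and Table 5 allow cobimetinib to continue after atezolizumab stops. If it continues for k days and the clock runs from the later drug, reporting closes k + 30 days after the last atezolizumab dose. With k = 0 the gap is as above; with larger k it shrinks. Footnote s works the other way: new therapy on day 14, for example, would close reporting on day 14 under Appendix 1 and on day 30 under Sections 5.3.1 and 5.4.2.2.

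**5. Scale of a missed event**
One patient is 1/20 = 5 percentage points or 1/40 = 2.5 points of a cohort rate. The documents give no rate of late immune-related events. As an assumption only, let p be the per-patient risk of an onset between day 31 and month 5. Expected events are n × p, and the chance of at least one is 1 − (1 − p)^n.

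| p | n = 20: expected; chance of at least 1 | n = 40: expected; chance of at least 1 |
|---|---|---|
| 1% | 0.2; 18% | 0.4; 33% |
| 5% | 1.0; 64% | 2.0; 87% |
| 10% | 2.0; 88% | 4.0; 99% |

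These count all late events. The number actually missed would be smaller, because related SAEs and deaths keep a route.

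**The case against.** The strongest reply is that the protocol does look after day 30. Section 3.1.1.1 says patients are followed after discontinuation to monitor adverse events, Sections 3.2 and 4.6.1 provide safety follow-up, and Section 5.3.1 has investigators ask about adverse events at each contact. Late related SAEs go onto the same Adverse Event eCRF with no end date, and Section 6.5 states no 30-day cut, so they can enter the tables. A late AESI that leads to hospital admission, or that the investigator judges medically significant, is an SAE and falls under Section 5.6 if believed related. The study is descriptive and hypothesis-generating.

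Most of this stands, and it limits the gap to the cases identified above. It does not close it: the follow-up statements set no reporting rule of their own, and both Section 5.6 and footnote s fall back on awareness plus suspected relatedness.

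A reader might infer from the 5-month rules that the protocol regards atezolizumab as active for 5 months, and might then calculate how much drug remains at day 30. The documents do not support that. They state no half-life and no duration of effect. The vaccine, contraception and pregnancy rules are precautions, the late sample is for PK and ADA, and the Appendix 8 remark concerns managing an existing toxicity. A reader might also infer that late serious events are lost altogether; the related-SAE route and the full capture of deaths show otherwise.

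**Conclusion.** The point holds as a limited gap in data collection. New non-serious AESIs starting after the window have no reporting route, and non-fatal late SAEs are reported only if known and believed related. AESI rates under Section 6.5 therefore under-capture late immune-related events. The direction follows from the text, provided some such events occur; the size cannot be derived from the documents.

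The conclusion does not rest on a half-life or on any claim about how long atezolizumab acts. It does depend on the clock: the gap after atezolizumab is smaller where cobimetinib continues and the later dose governs, and larger where footnote s governs and new therapy starts early. The conflict between footnote s and Sections 5.3.1 and 5.4.2.2 is a plain inconsistency and needs reconciling in any case. The change is worth making because it is cheap; it does not call the primary efficacy analysis into question.

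**What to change.** 1. In Sections 5.3.1, 5.4.2.2 and 5.6 and in Appendix 1 footnote s, state which drug's last dose starts the clock, and reconcile whether new anti-cancer therapy closes reporting.
2. In the same places, collect SAEs and AESIs regardless of attribution through the PK/ADA visit already scheduled after day 90, or the 3-monthly survival contact. Leave other adverse events at 30 days.
3. In Appendix 1, add an adverse-event mark to the PK/ADA visit and align footnote c with Appendix 2. The visit has no upper time limit, so record the date of the last adverse-event enquiry.
4. In Section 6.5, tabulate onset up to 30 days and later onset separately, flagging events that began after new anti-cancer therapy. The 30-day result stays visible.

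If the sponsor keeps 30 days, it should give the reason and label the AESI rates as covering treatment plus 30 days only.

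The cost is protocol wording, one table split and more reports to process, with no new visits. Some added events will be due to progression or subsequent therapy, and the reported AESI rate will be somewhat higher. This is a data-collection rule and changes no dose, treatment or stopping rule.
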